We hypothesize that therapy done at a low dose will produce the best cost-to-risk ratio for patients.

3. Research design and procedures

This study is designed as a randomized controlled trial with repeated measures.

Aim – the effect of exercise dose on pain: subjects will be randomly assigned to one of four exercise groups: 1.) no exercise (control); 2.) low dose exercise (3x/week); 3.) moderate dose exercise (5x/week); 4.) high dose exercise (10x/week).

The co-primary investigators (co-PI's) will be involved in the procedures listed below. Graduate research students will assist with recruitment, data collection, and data processing. A PhD student in the Biology department ([name]) will assume primary responsibility for data collection. The graduate students will be trained on all procedures involved in this study by the co-PI's. Prior to data collection, the prospective subjects will complete a full screening, using a checklist of the inclusion/exclusion criteria and the PAR-Q and AHA health questionnaires (see Instruments) to determine eligibility. The purpose of the study, the methods of data collection and all potential risks will be verbally communicated to prospective subjects at the

initiation of the first data collection session (Day 0) (Figure 1). Prospective subjects will be given an approved informed consent form to read and sign. Subjects will then complete the International Physical Activity Questionnaire long form (IPAQ-long) to assess baseline level of daily physical activity and the Social Interaction Anxiety Scale (SIAS) for a measure of participant's anxiety. The researcher will explain the questionnaires to subjects and will be available to answer any questions while the subjects complete these forms. Basic health information obtained from the subject will assess whether the subject has been diagnosed with any cardiac, respiratory, neurological or musculoskeletal disorder, chronic pain or currently has acute pain. Subjects who report any of the above medical diagnoses or pain during screening will be excused from participation in the study, but will receive compensation for attending the screening session. Any identifying information used to determine eligibility, including the checklist of inclusion/exclusion criteria and the health questionnaires, will be destroyed.

[figure not shown]

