based on well-established assays used in both healthy human participants and patients with chronic pain⁹. All assays involve either innocuous (non-painful stimuli) or acute noxious stimuli (painful stimuli) that do not damage tissue. Time between different tests will be >5 min to allow the subject to rest. Timing of testing on experimental days will be 5 minutes and 30 minutes following the completion of exercise or 30 minutes of rest (for control subjects and for all subjects on day 6). For all testing days order will proceed in the following manner. Training and description of each measure is as follows:

Cutaneous mechanical sensitivity assay¹⁰: Enrolled participants will be asked to sit in a chair (chair provided with arm-rests). Assay involves determining the sensitivity threshold for innocuous cutaneous stimulation. Stimulation is provided with standard sensory evaluator filaments (see equipment section below for image of filament). These are small nylon filaments each apply a single force (ranging from 0.008gram to 1.0gram). Before the start of the first experimental trial, subjects will be allowed to feel and manipulate the filaments. Starting with the smallest filament (0.008g; below the sensory threshold for human detection), 5 trials will be directed at the subject's forearm. During testing, subject is asked to look away from their forearm/calf. Experimenter will ask "Can you feel this" while the experimenter applies the filament to the subject's forearm or calf. With each filament, the experimenter will apply the filament 3 times in the "positive" trials. For the other 2 trials, the experimenter will not apply the filament but ask the subject, "Can you feel this?" These 2 "negative" trials will be randomly inserted with the 3 "positive" trials and are designed to test for false responses. If a subject detects ≥ 2 of the positive trials and 0 negative trials for a filament, that force will be the subject's "mechanical sensory threshold." For a single filament, if the subject detects < 2 of the real trials and/or > 0 of the false trials, the experiment will start another round of 5 trials with the next biggest filament until the sensory threshold is reached. Typical testing time for each body part (forearm and calf) is about 5 minutes.

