Mechanical pressure sensitivity assays^{10,12}: Assay involves determining the sensitivity threshold for painful pressure stimulation and then determining the quality and unpleasantness of that same pressure in a separate trial. Stimulation is provided with a standard clinical pressure algometer (see below instrument section). This device consists of a 0.5-2cm probe connected to a pressure meter. The probe is placed on the subject’s forearm or calf and pressure is gradually applied. Before the first training/experimental trial subjects will be allowed to apply the stimulus to themselves. During a trial, pressure will gradually be applied until the stimulus transitions from “innocuous pressure” to “painful pressure.” At this point, subject will say “stop” and the stimulus will be removed from the subject’s forearm/calf. When algometer is removed from the subject, the greatest pressure applied is automatically recorded in the device. This is the “pressure pain threshold” for the trial. 2 trials will be applied each to the forearm and calf in two distinct sites (on each limb) to avoid damage to a single area. After the pressure threshold has been determined for a subject, 1 additional trial on each limb will be applied (in a third testing site). In this trial, the subject will be asked to evaluate the intensity and unpleasantness of a pressure stimulus given for 3 seconds. This is done with a standard 0-10 visual analog scale (VAS). On the “intensity scale”, “0” is represented as “no pain” and “10” is represented as “the worst pain imaginable.” On the “unpleasantness scale”, “0” is represented as “not unpleasant” and “10” is represented as “the most unpleasant sensation imaginable.” During this trial, the experimenter will tell the subject that they are going to apply a painful stimulus to the subject and then ask the subject to evaluate that pain (on the two VASs). The exact stimulus will be matched to the subject’s pain threshold determined during the baseline trials (e.g. if baseline trials for forearm indicated a pressure threshold of 50 N then subject will be asked to evaluate the pain of that stimulus). During subsequent testing days (days 1, 3, 5, 6), the pressure pain threshold will be re-measured to determine if there is a change from baseline. For the intensity/unpleasantness testing, subjects will be tested on experimental days 1, 3, 5, 6 at their original baseline pressure threshold (from day 0) AND the threshold determined on each individual day. This will allow an analysis of change from baseline and pain at threshold for each experimental day.

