The heart rate monitor will be strapped to the subjects' chest to monitor HR throughout the exercise session. The purpose of monitoring HR is two-fold: 1.) to ensure the subject is working at a moderate level of intensity, and 2.) to ensure the subject is safely participating in physical activity with no abnormal or adverse changes in HR. Subjects will provide a rating of their perceived exertion on the Borg RPE scale before beginning the exercise task. Subjects will then be set-up to begin walking on the treadmill. Subjects will be reminded of the instructions for how to step onto the treadmill and the process for ramping up the speed as described in the training session. Once walking on the treadmill at the prescribed speed, subjects will be instructed to walk until the researcher returns (30 minutes). Subjects will be told that they can stop walking if they become excessively fatigued (≥ 17 on the Borg RPE scale) or experience symptoms of overexertion, such as lightheadedness and excessive sweating. The Borg RPE scale will be positioned in front of them for a visual reminder of the fatigue scale and the treadmill safety key will be secured to the subject's shorts. After 30 minutes, the researcher will return to the room. At this time, perceived exertion on the Borg RPE scale will be assessed again. The researcher will then slow the treadmill speed down to approximately 2 mph for a 2-minute cool-down. Pain measures will be completed as described above following completion of the treadmill walking at 5 minutes and 30 minutes.

Subjects will perform their exercise session alone, with no close supervision by study staff. To ensure safety during exercise, the subject will be monitored with 2 wireless video cameras. Camera 1 will be focused on the subject to visually observe the subject's performance and ensure there are no visual signs that the subject is over-exerted. Camera 2 will be focused on the treadmill interface to monitor real-time HR and ensure the subject does not adjust the speed. Video recordings from the cameras will not be saved and is only used to monitor the subject's physical response to exercise. Subjects will be unaware that they are being monitored via camera. All subjects will return on Day 6 to complete a final round of pain/sensory testing.

4. Instruments

Screening Questionnaires

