PARQ and You will be used to determine if a participant is not healthy enough to participate in the study due to a presence of a heart conditions, chest pain, dizziness, joint problems, and drug use.

AHA/ACSM Health Fitness Facility Preparticipation Screening Questionnaire collects past medical history, current health issues, and cardiovascular risk factors that would indicate exclusion from participation.

Physical performance

For all conditions, we will evaluate daily normal physical activity and intensity with a pedometer.

The International Physical Activity Questionnaire long version¹⁴ (IPAQ-long) will be used to obtain estimates of weekly physical activity. Based on subjects' responses, the total energy

expenditure for participation in different physical activities can be calculated. The total energy expenditure is used to categorize subjects based on the amount of vigorous, moderate, or low intensity activity they engage in.

The Borg RPE scale¹⁵ is used to collect a subjective measure of fatigue. The Borg RPE scale ranges from 6 (no exertion at all) to 20 (maximal exertion). This scale is based on expected heart rate during minimal, moderate, and vigorous intensity exercise. A subject who rates their exertion level as a 12 on this scale is working at a moderate intensity and should have a heart rate of 120 beats per minute (12×10).

All exercise sessions will be monitored using two wireless cameras (Dropcam Wireless Video Camera) to avoid influence of social observation while continuing to monitor subject's performance and physiological measures (HR) of exercise. Video will be transmitted via a secure Wi-Fi signal to a university-owned laptop computer. Either a PI or graduate student will view the real-time video to ensure subject's safety and continued optimal performance. Video will be transmitted via secure wireless signal to ensure confidentiality.

Pain measures –As described above, the three tests are for tactile sensitivity, thermal pain, and pressure pain.

Cutaneous Stimulators –

For cutaneous mechanical sensation, we will use standard von Frey filaments (Touch Test Sensory Evaluators; North Coast Medical). These filaments (ranging from 0.008g to 1.0g) are used to measure threshold for sensation to innocuous stimulation. See above for full description of assay.

Radiant Heat –

For radiant thermal heat measurements, we will use a standard “Hargreaves” apparatus (IITC Thermal Stimulus Apparatus) (see image to right).

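### No assessor blinding is described, and nothing keeps the Day 6 tester separate from the staff who run that subject's sessions, although Day 6 could be tested blind

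*Combined protocol and SAP*

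**What the plan says.** **Staffing (Section 3, opening paragraphs).** A PhD student "will assume primary responsibility for data collection". In addition, "Graduate research students will assist with recruitment, data collection, and data processing", and the co-PIs are involved in the procedures. "The graduate students will be trained on all procedures involved in this study".

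**Exercise sessions (Section 3, Exercise Session; Section 4).** The treadmill is run by an unspecified researcher: "The researcher will then slow the treadmill speed down to approximately 2 mph". For monitoring, "Either a PI or graduate student will view the real-time video".

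**Sensory tests (Section 3, assay descriptions).**
- Filaments: for each filament, "the experimenter will apply the filament 3 times in the" positive trials. Two negative trials are mixed in at random.
- Pressure: the probe goes on the "forearm or calf and pressure is gradually applied". No ramp rate is given. The subject calls a halt and the device stores the peak. For the ratings, the experimenter announces a painful stimulus and then asks for the scores.
- Heat latency: the device stops and times the trial when the limb is lifted.
- Second heat test: a constant 45°C block for 3 seconds, rated by the subject.

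**Primary time point.** Section 8 compares Day 6 with Day 0 as a percent change. Under Procedures in Section 3, randomization follows the screening and training session. "All subjects will return on Day 6 to complete a final round of pain/sensory testing"; nobody exercises that day, and all groups have the same 30-minute rest before testing.

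The document has no statement on blinding of assessors, participants or analysts.

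**The concern.** Every outcome in the battery rests on a subject's report, and several depend on how a person applies or introduces the stimulus. A tester who knows the group can press faster or slower, or prompt differently, without meaning to. On Days 1, 3 and 5 testing takes place before and after the exercise or rest session, so whoever tests then will normally know the group. If that person also tests on Day 6, the knowledge carries into the primary comparison. A systematic shift of this kind cannot be removed in the analysis, and a larger sample makes it more likely to be declared significant.

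The plan already guards against similar influences elsewhere: subjects exercise unattended under camera so that being observed does not affect them, and pedometer screens are covered. It describes no such protection for the primary outcome.

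**Working it through.** **1. Could Day 6 be tested blind?** Three statements, read together, say yes.
- Day 0 testing belongs to the session before randomization, so the baseline tester cannot know the group.
- Day 6 has no exercise and the same rest period in all four groups, so the procedure does not reveal the group.
- The one item carried forward is the Day 0 pressure threshold, needed for the Day 6 ratings. It can be passed on without the allocation.

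**2. Which tests are exposed?**

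| Test | Who controls the stimulus | Exposure |
|---|---|---|
| Pressure threshold | Operator ramps by hand, no rate stated | Greatest |
| Pressure ratings | Operator applies and announces the stimulus | Greatest |
| Filaments | Hand-applied, but fixed force, negative trials and a fixed pass rule | Less |
| Heat latency | Device stops and times | Least |
| 45°C ratings | Fixed temperature and duration | Least |

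The 1% ANOVA covers 7 tests per body site. The mechanical sensitivity test, which I take to be the filament test, uses a rank sum test at 0.05, so the figures in step 3 do not apply to it.

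**3. Illustrative size.** The plan has no figure for assessor bias to reproduce. The inputs from the documents are 4 groups, alpha 0.01 (Section 8), and a minimum of 10 and a goal of 15 per group (Section 5). The assumed input is a shift of b SD in each exercise group relative to control, with no true effect.

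With group means (0, b, b, b), Cohen's f = b√3/4 and the noncentrality is λ = 4n·f² = 0.75·n·b². The rejection probability is P(F > critical value), where F is noncentral with 3 and 4(n−1) degrees of freedom. The critical values are 4.377 (n = 10) and 4.152 (n = 15).

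| b (SD) | λ, n = 10 | Rate, n = 10 | λ, n = 15 | Rate, n = 15 |
|---|---|---|---|---|
| 0 | 0 | 1.0% | 0 | 1.0% |
| 0.1 | 0.075 | 1.1% | 0.113 | 1.2% |
| 0.2 | 0.300 | 1.5% | 0.450 | 1.8% |
| 0.3 | 0.675 | 2.2% | 1.013 | 3.1% |
| 0.5 | 1.875 | 5.3% | 2.813 | 9.0% |

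If the bias instead rose with dose, as (0, b/3, 2b/3, b) with b = 0.5, the rates would be 3.9% (n = 10) and 6.3% (n = 15).

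**4. Cost of changing the tester at Day 6 only.** Differences between testers would then enter the Day 6/Day 0 ratio. Suppose (an assumption) that they add a component with SD s, in units of the outcome SD. Then f shrinks by the factor 1/√(1 + s²). At alpha 0.01, 80% power needs f = 0.673 with n = 10, or 0.534 with n = 15.
- s = 0.3: √1.09 = 1.044, so f falls to 0.645 or 0.512, and power to about 75%.
- s = 0.5: √1.25 = 1.118, so f falls to 0.602 or 0.478, and power to about 67%.

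Using the same tester on Day 0 and Day 6 largely avoids this loss.

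**The case against.** A reader might infer that one student does all the testing and therefore also runs the exercise for the same subjects. The documents do not say so. Responsibility is primary, not sole; others assist; the treadmill operator is simply a researcher; and the video viewer is a PI or graduate student. What is supported is that nothing prevents the overlap. Nor can silence in a protocol summary form be read as a decision against blinding.

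A reader might also treat the whole battery as hand-operated pain tests. It is not. The filaments test innocuous touch at fixed forces, heat latency is device-timed, and the 45°C stimulus is fixed. Even for pressure, the subject calls the endpoint and the device records it. This objection stands: it narrows the exposure mainly to the pressure tests, but does not remove it.

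The size is also open to challenge. The shift is assumed, at 0.1-0.2 SD the inflation is slight (1.1-1.8%), and an equal shift in all exercise groups is a guess. The plan's only stated hypothesis favours low dose on a cost-to-risk ratio, which does not fix the pattern of a tester's expectations. That stands too, so the figures are illustrative only.

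Finally, headcount and rosters are not given, every exercise session needs a live monitor, and one group has ten sessions in five days. Feasibility with existing staff is therefore inferred, although several people are to be trained on all procedures.

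**Conclusion.** The point holds as a weakness that is cheap to correct, not as a demonstrated bias. The protocol describes neither assessor blinding nor separation of roles at the primary time point, although its own schedule would allow both. Under the assumed 0.1-0.5 SD shift in all three exercise groups, the false-positive rate of an affected 1% ANOVA would be 1.1-5.3% with 10 per group or 1.2-9.0% with 15. These rates should not be applied to every test in the battery: they fit the pressure outcomes best, the heat outcomes least, and the rank sum test not at all. The direction is firmer than the size: under this model, any systematic shift between groups pushes the rate above 1%, and more so as the sample grows.

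**What to change.** State in Section 3 that:
- each subject's Day 0 and Day 6 tests are done by the same trained member of the existing team;
- that person takes no part in the subject's Day 1-5 sessions, including video monitoring, and has no access to the allocation;
- the Day 0 pressure threshold is passed on without the group;
- subjects are asked not to mention their schedule to the tester.

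The sample size and the analysis do not change. The cost is scheduling: one person must be available for both days and kept away from the sessions between. The sponsor should confirm that staffing allows this.

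The rule blinds only the tester, and only for the primary comparison. Subjects will still know their group, so their own expectations can still affect their responses, and the Day 1, 3 and 5 tests remain unblinded. Both limits should be stated when results are reported.

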Radiant heat sensitivity assay¹¹: Assay involves determining the sensitivity threshold for painful thermal stimulation. Stimulation is provided with a radiant heat device¹¹. This device uses a focused light beam to slowly heat a subject's skin. Before the start of the training/ experimental trials, subjects will be shown device and allowed to feel the stimulus with their hand. Subject will be asked to rest their forearm or calf on a room temperature glass plate. Using a mirror, the light source will be positioned under a marked area on the subject's forearm or calf. Subjects are told to raise their leg or arm when they feel the stimulus transition from "innocuous warmth or heat" to "painful heat." When the leg or arm is raised from the surface of the glass, the thermal stimulus automatically stops and the time since the beginning of the trial is recorded as "latency to respond." Each trial lasts for a maximum of 20 seconds. The device is set so that typical withdrawal thresholds occur at approximately 10 seconds into the trial. The temperature on the glass at this point is $\sim 47^{\circ}\text{C}$ (121°F). The maximum temperature of the trial at the 20 second cutoff time point is 50°C which is well below the temperature that causes tissue damage in humans. For each limb, two trials will be completed in two distinct marked areas to avoid re-testing at a single site. Total testing time (2 trials on forearm and 2 trials on calf) is < 5 minutes.

A second assay will be used to evaluate the quality and unpleasantness of thermal pain. Each subject will receive a constant 45°C stimulus. 45°C is a standard temperature that is the typical minimal stimulus necessary to feel thermal pain. Stimulus (3cm x5cm heating block) will be applied for 3 seconds. Immediately following stimulus, the subject will be asked to evaluate the intensity and unpleasantness of the pain. This is done with a standard 0-10 visual analog scale (VAS). On the "intensity scale", "0" is represented as "no pain" and "10" is represented as "the worst pain imaginable." On the "unpleasantness scale", "0" is represented as "not unpleasant" and "10" is represented as "the most unpleasant sensation imaginable."

Example instructions for intensity VAS – *“Please use the scale below to tell us how intense your pain is. Place an “X” on the scale that best describes the intensity of your pain.”*

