Pressure Algometer –

For pressure pain testing, we will use a standard mechanical pressure algometer (Wagner Instruments).

Anxiety measures

All groups will be assessed for anxiety with questionnaire methods using the Social Interaction Anxiety Scale (SIAS)¹⁶. The SIAS measures anxiety with respect to social interactions. It is one of the more often-used self-report measures of social anxiety, with numerous evidence-based studies demonstrating its reliability and construct validity¹⁷. The SIAS contains 20 items which are rated from 0 (not at all characteristic or true of participant) to 4 (extremely characteristic or true of participant). Items are self-statements describing one's typical cognitive, affective, or behavioral reaction to a variety of situations requiring social interaction in dyads or groups (e.g., going to a party, talking to an attractive member of the opposite gender, expressing one's feelings).

5. Sample selection and size

Healthy adults will be recruited for participation in this study. The PAR-Q and You form and the AHA screening questionnaire will be administered during the screening process to determine whether potential subjects meet the inclusion/exclusion criteria.

Inclusion criteria include:

- Between age 18-40
 - Normal BMI (18.5-25)
 - HR 60 to 100
 - BP less than or equal to 140/90
- *HR and BP will be taken as part of the screening process to determine eligibility and also taken at the beginning of each exercise session.

Exclusion criteria include as indicated by the PAR-Q and You and AHA screening forms:

- Age less than 18 or greater than 40 years
- Cardiac, respiratory, neurological or musculoskeletal disease
- Acute pain
- Chronic pain condition
- Diabetes
- BMI ≥ 25.1 or ≤ 18.4
- Regular participation in high intensity athletic/sporting activities
- Sedentary
- Anxiety or depression disorders.
- Tape allergy
- Currently pregnant

A power analysis of pain outcome indicates that a minimum of 10 people/condition will be sufficient to detect statistical differences in our primary dependent variable (pain sensitivity), but to account for variability, our recruitment goal is 15 people/condition. When 10 participants per group have completed the study, a preliminary analysis will be conducted for statistical power, if we reach 0.80, recruitment will stop.

6. Recruitment of subjects

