The collection of data has been described in detail under "Procedures". The primary outcome is a change in Quantitative Sensory Testing. This includes a series (8) of Quantitative Sensory Tests measured at baseline and at the completion of the 1-week intervention period. These tests are measured at two sites (calf and forearm). Significant differences between groups for 7 of the tests (per body site) will be identified using a one-way ANOVA comparing percent change from baseline (post-test (i.e. day 6)/baseline test (i.e. day 0)). Given the number of statistical tests that will be required for the primary outcome measurements, $p < 0.01$ will be utilized for each body site. An additional test for mechanical sensitivity will be measured at each site using a rank sum test at $p < 0.05$.

The secondary outcomes for this study include (1) HR during exercise, (2) Borg RPE before and after exercise and (3) testing "acute" effects of exercise on QST testing. HR during exercise and Borg RPE are measured to make sure that exercise causes a change in HR and/or perceived exertion. HR and Borg RPE data will be analyzed using percent change from start of exercise (post-exercise/pre-exercise) with two-way ANOVA for 3 treatment groups (3-day, 5-day, 10 day) across time (day 1, 3, 5) with an adjusted p value of $p < 0.03$. Control group will not be included in that analysis as HR was not measured on the control days and perceived exertion is at "0" on all days. For acute effects of exercise, participants were given 8 QST tests (on each forearm and calf) 5 min and 30 min after each exercise (or control session) on days 1, 3, and 5. Significant differences between groups for these tests (per body site) will be identified using a two-way MANOVA comparing percent change from baseline (post-exercise/baseline test (i.e. day 0)) across the three days (day 1, day 3, day 5) and at the 5 min and 30 min time QST measuring point. Given the number of statistical tests ($n=8$) that will be required for the QST secondary outcome measurements, $p < 0.01$ will be utilized for each body site.

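### At least four of the seven primary ANOVAs per site compare Day 6/Day 0 ratios of 0-10 ratings given at or near pain threshold, where the ratio can be undefined or unstable; a model adjusted for the Day 0 rating is better

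*Combined protocol and SAP*

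**What the plan says.** **Heat ratings** (Section 3, Radiant heat sensitivity assay). Every subject receives the same 45°C block for 3 seconds and rates intensity and unpleasantness from 0 to 10. The protocol explains that "45°C is a standard temperature that is the typical minimal stimulus necessary to feel thermal pain". Zero on the intensity scale means absence of pain.

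**Pressure ratings** (Section 3, Mechanical pressure sensitivity assays). The rated pressure is matched to the subject's own threshold, the point at which pressure turns painful. On later days subjects are "tested on experimental days 1, 3, 5, 6 at their original baseline pressure threshold (from day 0" and also at that day's own threshold. The risk text in Section 10 adds that applied pressure never exceeds the pain threshold.

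**Analysis** (Section 8). On the primary outcome: "This includes a series (8) of Quantitative Sensory Tests measured at baseline and at the completion of the 1-week intervention period". Then: "Significant differences between groups for 7 of the tests (per body site) will be identified using a one-way ANOVA comparing percent change from baseline", defined as Day 6 over Day 0, at p < 0.01. The eighth measure is handled apart: "An additional test for mechanical sensitivity will be measured at each site using a rank sum test". The eight tests are not listed by name, and nothing is said about a Day 0 score of zero.

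**The concern.** The research question is whether exercise reduces pain, so the expected movement in a rating is downward. A rating taken where pain begins, on a scale whose zero is no pain, may have little distance to fall. Dividing by such a score makes matters worse. A Day 0 rating of 0 gives no ratio at all. A move from 0.2 to 0.6 counts as 0.6/0.2 = 3.0, while the same 0.4-point move from 4.0 to 4.4 counts as 4.4/4.0 = 1.1. A few subjects with very low Day 0 scores can then dominate the group variance. At stake is whether a real reduction in rated pain would be detected, and whether a null on the ratings would be misread as absence of analgesia.

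**Working it through.** **1. Count of ratings in the primary set.** Measures described per site in Section 3: filament threshold (rank sum), heat latency, pressure pain threshold, two heat ratings, and two pressure ratings at the Day 0 threshold, making 7. The two ratings at the same-day threshold make 9. Neither equals the stated 8. Only heat latency and pressure threshold are ANOVA measures that are not ratings, so subtraction gives 7 − 2 = 5 ratings among the seven ANOVAs. Counting only the heat ratings and those at the Day 0 pressure gives 4. The count of at least four of seven holds either way.

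**2. The plan's own sample-size figure.** Section 5 says that "a minimum of 10 people/condition will be sufficient to detect statistical differences in our primary dependent variable (pain sensitivity"), with a goal of 15. It gives no effect size, SD or alpha, so the figure cannot be reproduced. For 80% power in a four-group ANOVA at alpha 0.01, the noncentral F needs Cohen's f = 0.67 at 10 per group or 0.53 at 15.

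**3. Assumed inputs.** The protocol gives no rating mean, SD or share of zeros. Assumed: 15 per group (the recruitment goal); alpha 0.01 (Section 8); latent rating normal with SD 1 or 1.5, recorded as 0 when below 0; Day 0 to Day 6 correlation 0.7; falls of 0, 0.6, 0.8 and 1 SD in control, low, moderate and high groups; subjects with a zero Day 0 score dropped from the ratio.

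**4. Benchmark with no floor.** The mean fall is 0.6 SD, so the squared deviations sum to 0.36 + 0 + 0.04 + 0.16 = 0.56.
- Difference score: variance 2(1 − 0.7) = 0.60; noncentrality 15 × 0.56/0.60 = 14.0; power 68%.
- Day 0 rating as covariate: variance 1 − 0.7² = 0.51; noncentrality 15 × 0.56/0.51 = 16.5; power about 78%, slightly optimistic because chance baseline imbalance is ignored.

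**5. With the floor.** The share of zero Day 0 scores is Φ(−mean/SD). Power is by simulation; differences of about three points should be ignored.

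| Day 0 mean | Zero at Day 0 (SD 1 / SD 1.5) | Power, Day 6/Day 0 ratio | Power, Day 0 rating as covariate (ANCOVA or rank ANCOVA) |
|---|---|---|---|
| 0.5 | 31% / 37% | 20-25% | 48-53% |
| 1 | 16% / 25% | 27-33% | 58-65% |
| 2 | 2% / 9% | 37-48% | 68-75% |
| 3 | 0.1% / 2% | 46-62% | 70-77% |

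At a mean of 0.5 and SD 1, the ratio loses about 15 × 0.31 = 4.7 subjects per group. At mean 1 and SD 1, power is 33% for the ratio, 42% for a floored difference and 62-65% with the covariate.

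**6. Reading the table.** At a mean of 3 there are almost no zeros, yet the ratio still trails. That gap comes from the noise of the ratio and the efficiency of the covariate, not from the floor. At 0.5, covariate adjustment recovers much of the loss but stays well below its 78% benchmark. Adjustment reduces the floor problem without removing it.

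**The case against.** **No baseline ratings are given.** That they lie near zero is an inference, and the protocol offers reasons they may not. The threshold is the greatest pressure reached when the subject says stop on a rising stimulus; it is then applied for 3 seconds after a warning that it will be painful. This stands, and is why the size is shown as a range.

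**Unpleasantness is different.** The example instructions in Section 3 tell subjects that mild pain can still be very unpleasant. This also stands: the floor argument is firmest for intensity, which is half of the four ratings.

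**Heat threshold.** A reader might infer from the typical radiant withdrawal at about 47°C that 45°C is below threshold. The documents do not support that. The 47°C is a glass temperature under a light beam at about 10 seconds; the 45°C is a contact block for 3 seconds. The 47°C is also paired with 121°F, although 47 × 9/5 + 32 = 116.6°F and 121°F is 49.4°C, so that passage must be reconciled. Moreover, 45°C is the typical threshold, not each subject's, so some subjects will rate it well above zero.

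**The inputs drive the loss.** With mean 0.5 but SD only 0.25, floored differences have 64% power against 68% without a floor. This is a fair limit: what matters is the spread relative to the mean.

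**Other primary tests are unaffected.** Heat latency (typically 10 s, cutoff 20 s) and pressure threshold have room to rise, and each measure is tested separately. A null on the ratings cannot cancel a positive threshold result.

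**Conclusion.** The point holds as a weakness in how the ratings are analysed, with a conditional floor behind it. At least four of seven primary ANOVAs per site use ratings at or near threshold, and the Day 6/Day 0 ratio suits them poorly. Under the stated assumptions, adjusting for the Day 0 rating raises power by roughly 15 to 30 percentage points: the lower ends of the ranges differ by 28, 31, 31 and 24, the upper ends by 28, 32, 27 and 15. The absolute loss is largest at means of 0.5-1. A higher mean or smaller spread shrinks the floor.

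Two stronger readings are not supported. One is that the ratings are insensitive and must leave the primary set. With heat latency and pressure threshold at two sites as the only primaries, the strictest Holm level would be 0.05/4 = 0.0125 instead of 0.01, a gain of about three points (68% to 71%) in the no-floor difference-score scenario. Set against losing the rated dimension of pain, that is a matter of preference. The other is that the floor persists in full under any analysis; the covariate results show otherwise.

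**What to change.** In Section 8, for all 0-10 ratings, replace the one-way ANOVA on percent change with an ordinal (or rank-based) model of the Day 6 rating, with group as factor and the Day 0 rating as covariate. Subjects with a Day 0 score of zero then stay in the analysis. Report the share of zero ratings by group and day. State that a null on the ratings alone is not evidence of no analgesia where zeros are common. Listing the eight tests by name would show which analyses the change covers.

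The cost is a little more analysis work, and the result is no longer a percent change. The power figures are for ANCOVA and rank ANCOVA; an ordinal model was not simulated, and no model recovers information below zero. No new data are needed. Because parts of Section 8 are in the past tense, some data may already exist, so the change should be dated and made before groups are compared, or labelled as made afterwards. Whether the ratings stay primary is for the investigators, and no stimulus level is proposed.
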